 - Pain of procedure: To assess pain of procedure, we will use the 11 point Numeric Pain Rating Scale (NPRS). We expect that the patients receiving 10 injections will have less pain associated with the procedure. The patients will rate their level of pain immediately following the completion of bladder injections by selecting a whole number from 0 to 10 that represents their level of pain (0 is no pain at all and 10 is the most severe pain) during the procedure. This scale has been validated, and correlates similarly to other pain scales [7].
- Secondary endpoints: Secondary endpoints to be assessed will be efficacy, OAB symptoms (nocturia, urgency, and frequency), post void residual volume (PVR) at 2 weeks and 12 week post-procedure, disease specific bother, health related quality of life (HRQoL), the patient's perceptions of change, and adverse events as detailed below:
 - Efficacy: The reduction in mean urge incontinence episodes which will be calculated by averaging the amount of urge urinary incontinence episodes over 3 days as recorded in a bladder diary. Success will be defined as a greater than 50% reduction in urge incontinence episodes after intradetrusor Botox® based on 3-day bladder diaries collected at baseline and 12 weeks post-injection. This outcome measure is consistent with results reported in previous trials involving Botox® for overactive bladder [6].
 - Disease specific bother and HRQoL: To assess OAB symptoms other than incontinence and impact on quality of life, we will administer the Overactive Bladder Questionnaire Short Form (OABq-SF) at baseline, at 2 weeks, and at 12 weeks post-procedure. This is an abbreviated version of the Overactive Bladder Questionnaire (OABq) developed to evaluate the bother and health related quality of life for patients with overactive bladder. The OAB-SF contains 6 items to assess symptom bother and 13 items to assess HRQOL. This questionnaire is commonly used, and has been validated for use in clinical practice [8].
 - PVR at 2 weeks and 12 weeks: To measure PVR at 2 weeks and 12 weeks, we will use a bladder scanner which measures volume based on ultrasound. The provider may also chose to measure PVR by straight catheterization at his or her discretion.
 - Patient's Global Impression of Change (PGIC) scale: In order to help determine the clinical significance of change, we will utilize the PGIC scale [16] administered at 2 weeks and 12 weeks post-injection.

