After consenting to enrollment in the study, the patients will be scheduled for Botox® injections in the office. Randomization will be performed using random sequence number generation in blocks of 10 with randomization assignment concealed in sequentially numbered opaque envelopes. Randomization will be performed before the study startup by the coordinator using online available tool (sealed envelope). Envelopes with 50% carrying 10 injections instructions, and 50% carrying 20 injections instructions are prepared in advance, sealed, numbered 1 to 50, and stored in a locked cabinet at the Urology clinic at [name]. Three envelopes will be carried to the Greensboro Wake Health System during coordinator's scheduled clinic days. And then coordinator will bring those packets back to the [name] Urology clinic on a regular base. On the day of the procedure, the provider will select the next numbered envelope that will contain the randomization assignment for the number of injections. Subjects will be blinded to the randomization result. All patients will undergo a urinalysis prior to the procedure. If there is concern for an acute, untreated urinary tract infection, the patient does not undergo the procedure, and is treated with antibiotics while a urine culture is sent. All participants will be given preoperative antibiotics (except aminoglycosides). 100 units of Botox® will be combined with 20 cc saline for the purposes of 20 injections, or 100 units of Botox® will be combined with 10 cc of sterile saline for the purpose of 10 injections. Lidocaine Jelly locally. And the bladder will be instilled with 30ml of Marcaine and 5ml of NaHCo3 solution through a catheter for at least 15 minutes prior to the procedure. Cystoscopy with either a rigid or flexible cystoscope (per surgeon preference) will be performed using sterile technique. The Botox® will be injected in a grid like pattern avoiding the trigone as seen below. Study patients do not know the number of injections received in the bladder. There are two providers in the room for each procedure. Injection counting will be verbalized as Injection 1, Injection 2... to up to Injection 20 by non-injecting provider. A patient and a provider who is injecting will hear total of 20 counts. Providers will know the randomization prior to procedure, and a decision will be cleared between two providers whether to account pseudo injection at odd or even number for patients receiving 10 injections. A patient randomized to 10 injections will receive 10 injections at alternate count. All patients will be informed in advance about the procedure at the time of consenting. The patient will be allowed to void on her own postprocedure. Immediately after the procedure, the patient will receive a questionnaire to rate the pain of procedure using the numeric pain scale. The patient will then be discharged to home. Figure 1: Diagram showing sites of injections for patients undergoing 10 injections of 100 units of Botox®.

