- Exclusion Criteria:
 - 1. Male gender
 - 2. Neurological conditions (Examples: Cerebral vascular accident within 6 months prior to treatment, Parkinson's disease, Multiple Sclerosis, and Spina Bifida).
 - 3. Acute urinary tract infection
 - 4. Treatment with Botox® toxin for other conditions
 - 5. Allergy to Botox® toxin
 - 6. Hematuria that has not been worked up
 - 7. Known bladder malignancy

- 8. Previous history of bladder augmentation
- 9. Currently pregnant (with no plans to become pregnant within 6 months of enrollment) or breastfeeding
- 10. Currently taking aminoglycoside antibiotics
- 11.PVR >150 cc (measured by bladder scan or by catheterization) prior to enrollment
- 12. History of bladder pain syndrome.
- Sample Size:
 - This study is unique as there are no previous trials assessing pain of procedure associated with intravesical administration of bladder Botox. To calculate sample size in the study, we will assume an effect of size of 1. We expect that patients receiving 20 injections will be within the moderate pain range (between 5 to 7 on the NPR scale). Therefor we will assume a mean NPR rating for patients receiving 20 injections would be 6 with a standard deviation of 2. Patients receiving 10 injections will be expected to have less pain and be in the mild pain range (from 1 to 4 on the NPR scale). Based on this, we would need 16 patients in each group. Accounting for a 20% drop out rate, we would need to accrue 20 patients in each group.

• Statistical Analysis:

- 1. Primary endpoint: Each patient will be asked to rate her pain level of procedure by completing the NPRS immediately after her procedure. The mean NPRS score of each group (10 injections vs 20 injections) will be calculated and compared using a paired T test.
- 2. Secondary endpoints

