 - Each patient's mean number of urge urinary incontinence episodes will be calculated by averaging the number of urge urinary incontinence episodes collected over 3 days as recorded on a bladder diary. This will be calculated pre-intervention at baseline and at 12 weeks. As previously described, "treatment success" is defined achieving greater than 50% reduction in the number of urge urinary incontinence episodes at 12 weeks after treatment with Botox®. A "treatment failure" will be defined as achieving less than 50% reduction in the number of urge urinary incontinence episodes at 12 weeks after treatment with Botox®. A "treatment failure" will be defined as achieving less than 50% reduction in the number of urge urinary incontinence episodes at 12 weeks after treatment with Botox®. Our hypothesis is that there will be more significantly "treatment responders" in patients receiving 20 injections compared to 10 injections. To assess for clinical significance Chi square (X²) will be used.

- OABq-SF and PGIC collected from the group receiving 20 injections and the group receiving 10 injections. The mean will be calculated for each of the outcomes and for each of the groups. The result will be compared using paired t-test.
- We will compare the mean number of patients with urinary retention and UTIs in patients in both groups (those receiving 20 injections and those receiving 10 injections). To test for significance we will use the t-test.

Interventions and Interactions

- This study will use the FDA approved dose for refractory overactive bladder which is 100 units of onabotulinum toxin A (Botox®).
- Per surgeon preference, a flexible cystoscope or a rigid cystoscope will be used to inject the Botox® in the wall of the bladder.
- Injections will be in a grid-like fashion.
- We will use a 3 day bladder diary obtained from the International Urogynecological Association (IUGA) for baseline and 12 week follow up. (Appendix 1)
- Immediately after the treatment, patients will be asked to rate their pain using the Numeric Pain Scale. Please see appendix.
- Patients will be assessed for adverse events, symptom specific and global quality of life using the form in the appendix.
- All surveys will be handed to the patients by nursing. Patients will fill out the forms before seeing a physician.

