Appendix 1: IUGA 3 Day Bladder Diary to be completed by the patient.

Protocol version: 1 Page 14 of 21

Please rate the pain that you experienced during this procedure using the scale below.

Answer (Please write a number from 0 to 10):

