Official Title: A Randomized Clinical Trial of 100 Units of Intradetrusor Onabotulinum Toxin A for Refractory Overactive Bladder - Is 10 Injections Less Painful Than 20 Injections?

NCT04124939 Date: 7/31/23

Statistical Analysis - 10 vs 20 Botox Injections

Standard descriptive statistics were used to compare demographic and clinical characteristics. Frequency and percentages were reported for categorical data. Chi-square and fisher exact test for categorical variables and student t-test or Mann-Whitney U test for continuous variables were used to assess significant differences between the groups. Statistical analysis was performed on R Software.

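### The plan does not require the cystoscope type to be chosen before the provider learns the arm, although the primary pain score covers the whole procedure

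*Protocol*

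**What the plan says.** **Instrument.** The Design part of the protocol's Methods and Measures states: "Cystoscopy with either a rigid or flexible cystoscope (per surgeon preference) will be performed using sterile technique". Interventions and Interactions repeats the rule: "Per surgeon preference, a flexible cystoscope or a rigid cystoscope will be used to inject". Neither place says when the choice is made.

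**Timing of allocation.** The same Design text says: "On the day of the procedure, the provider will select the next numbered envelope". On blinding it says: "Providers will know the randomization prior to procedure". Only the patient is blinded, with a spoken count to 20 in both arms.

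**Outcome.** Under Objectives, the patient picks one whole number "that represents their level of pain (0 is no pain at all and 10 is the most severe pain) during the procedure". The form in Appendix 2 asks: "Please rate the pain that you experienced during this procedure using the scale below". Neither separates injection pain from the rest of the procedure.

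**Safeguards and analysis.** Randomisation is in blocks of 10, with no stratification stated. The Calendar of Events has no entry for scope type. Both documents plan plain two-group comparisons of the score. The SAP adds: "Standard descriptive statistics were used to compare demographic and clinical characteristics". It does not list those characteristics.

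**The concern.** Randomisation balances what is settled before allocation. It does not protect a choice that may be made afterwards by someone who knows the arm. Here that choice concerns the instrument, and the instrument belongs to the event whose pain is scored. Blinding the patient does not close the gap, because a scope could affect pain whatever she believes about her arm.

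Two things would both have to be true for harm: scope use differs systematically between arms, and scope type changes the score. Part of the measured difference would then reflect the instrument and not the number of injections. The direction is unknown, so the effect could be a false difference or a real one hidden.

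**Working it through.** **1. The plan's own figure.** The Sample Size section assumes "a mean NPR rating for patients receiving 20 injections would be 6 with a standard deviation of 2" and an effect size of 1, which is 1 × 2 = 2 NPRS points. It states no alpha, sidedness or power. With the usual values assumed (two-sided 0.05, 80%), the normal formula gives:

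n per arm = 2 × (1.960 + 0.842)² / 1² = 15.7, rounded up to 16.

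With 20% dropout, 16 / 0.8 = 20. Both stated figures are reproduced, and this point disputes neither. Power of an independent-groups t test for 2 points is 86.9% at 20 per arm and 78.1% at 16.

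**2. Formula for the shift.** Shift in the arm difference = g × q. Here g is the effect of scope type on NPRS, and q is the difference between arms in the share treated with one scope type. The documents give neither. Assumed ranges: g = 0.5, 1 or 2 points; q = 0.20 or 0.30.

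**3. Consequences.** These come from the noncentral t distribution with SD 2 and a two-sided 0.05 test. The noncentrality is the difference divided by 2 × √(2/n): the denominator is 0.632 at n = 20 and 0.707 at n = 16. For the false-positive rate the difference is the shift alone. For power it is 2 minus the shift, the case where the shift runs against the true effect.

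| g | q | Shift | False positives, 20 per arm | False positives, 16 per arm | Power, 20 per arm | Power, 16 per arm |
|---|---|---|---|---|---|---|
| any | 0 | 0 | 5.0% | 5.0% | 86.9% | 78.1% |
| 0.5 | 0.20 | 0.10 | 5.3% | 5.2% | 83.3% | 73.9% |
| 0.5 | 0.30 | 0.15 | 5.6% | 5.5% | 81.3% | 71.6% |
| 1 | 0.20 | 0.20 | 6.1% | 5.9% | 79.2% | 69.3% |
| 1 | 0.30 | 0.30 | 7.5% | 7.0% | 74.5% | 64.3% |
| 2 | 0.20 | 0.40 | 9.5% | 8.5% | 69.3% | 59.1% |
| 2 | 0.30 | 0.60 | 15.2% | 13.0% | 57.8% | 48.3% |

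**4. What a 10% false-positive rate would take.** At 20 per arm it needs a shift of 0.423 points. That is a difference in scope use of 0.423/0.5 = 85 percentage points for a 0.5-point effect, 0.423/1 = 42 for 1 point, or 0.423/2 = 21 for 2 points.

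**5. If scope choice is unrelated to arm.** Then q is zero apart from chance, and the expected shift is zero. A simulation of 40,000 trials (20 per arm, half with each scope, total SD 2) rejected a true null in 5.0%, 5.0% and 5.2% of trials for g = 0.5, 1 and 2. Chance imbalance is therefore already covered by the unadjusted test.

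**The case against.** The strongest reply is that harm needs two premises and the documents support neither. Leaving the instrument to the surgeon most naturally describes an operator's habit, which has nothing to do with a randomised envelope. No reason is given why anyone would change instrument for 10 injections as against 20. The anaesthetic preparation, the injection grid and the spoken count to 20 are common to both arms. The operator has to know the arm, so any discretionary element of technique is open to the same remark. The largest figures in the table use a 2-point scope effect, as large as the whole planned treatment difference.

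Most of this stands, and it limits the point. A reader might infer that the scope is chosen after the envelope is opened, or that the comparison is biased. The documents support neither: they are silent on when the scope is chosen and on whether it affects pain. Nor can one infer that scope was never compared between arms, since the SAP does not list its clinical characteristics.

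The reply does not supply the missing safeguard. An unblinded operator keeps a free choice within the scored event, and closing it takes one recorded line. That other discretionary elements remain open is no reason to leave this one open.

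**Conclusion.** The concern holds as a minor, preventable risk and not as a demonstrated bias. The plan should require the scope choice to precede knowledge of the arm, and it does not.

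If preference is fixed habit, the effect is nil. With an assumed scope effect of up to 1 point and a 20 to 30 percentage-point difference in use, false positives at 20 per arm stay at or below 7.5%, and power for the planned difference stays at or above 74.5%. Anything materially worse requires a scope effect near 2 points or a much larger difference in use. All these figures rest on assumed scope effects and scope mixes, SD 2 and a two-sided 5% test.

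A reader might also conclude that the primary analysis must be stratified or adjusted for scope. That does not follow: an unadjusted comparison is not a fault here, and the planned sample size need not change. Confidence is medium: the absence of the safeguard is clear from the text, but its practical effect is unknown.

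**What to change.** Add one step to the procedure. Before opening the envelope, the provider writes the intended scope on the sealed envelope or on a procedure-day form, with the choice left entirely to the surgeon. Record the scope actually used afterwards. Report scope used, and departures from the declared scope, by arm. If the declared scope is followed, scope cannot depend on arm.

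Keep the unadjusted comparison of NPRS as primary, in its independent-groups form. The SAP names such tests; the paired test in the protocol's Statistical Analysis does not fit two separate groups. Adjustment for the declared scope is optional and serves precision only. In the same simulation, power for a true 2-point difference was 86.6% to 86.7% unadjusted, and 86.2%, 88.0% and 93.8% adjusted for scope effects of 0.5, 1 and 2 points. It helps materially only if the scope effect is large, and it does not correct for departures.

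Cost: one or two recorded lines per patient and one table, with no extra patients, visits or staff and no change to the envelope list.

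The SAP is dated 7/31/23 and written in the past tense, so enrolment may be complete. In that case only a table of scope used by arm, taken from procedure notes where available, is still possible. Any adjustment for scope used should then be a sensitivity analysis only, because the scope may have been chosen after allocation.

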Adverse events: Specific to intradetrusor injections of Botox®, the most common adverse events are urinary retention requiring intermittent catheterization (approximately 4%) [9] and urinary tract infections (approximately 15.5%-35%) [10]. Patients will be closely monitored for urinary tract infections as they will undergo urinanalysis and assessment of symptoms at their post-operative visits.

Methods and Measures

- Design:
 - This study is a randomized clinical trial to assess whether or not 10 injections of 100 units of intradetrusor Botox® toxin is perceived as less painful compared to 20 injections of 100 units of intradetrusor Botox® toxin for the treatment of refractory OAB. Refractory OAB is defined as persistent urinary frequency and urgency despite behavioral modifications, failing a trial of 2 medications (anticholinergics or beta 3 agonists), have a contraindication to the medications, or are unable to tolerate medications due to allergies or side effects.
 - The primary outcome will be assessed by the patient completing the pain of procedure questionnaire, the NPRS, to be completed by the patient immediately after the procedure. The patient will receive the questionnaire from the nurse or medical assistant after the provider has performed the procedure. We will then compare mean value of the NPRS for the 10 injection group to the 20 injection group.
 - Efficacy will be assessed by comparing study participant's reduction in urge urinary incontinence episodes based on a 3 day voiding diary to be shared by the participant at baseline and 12 weeks post-procedure. This diary is dispensed to all patients during their visit prior to procedure visit as a part of standard of care. If subjects demonstrate a 50% reduction in urge incontinence episodes on a 3-day bladder diary, they will be categorized as "treatment success" whereas those who do not will be categorized as "treatment failure." This dichotomous outcome will define efficacy as a secondary endpoint.

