 - All eligible participants will be considered for the study. Patients will be counseled about the study in the office setting. Upon enrollment, patients will share a 3-day voiding diary. Diary is dispensed to all patients when they decide to undergo injection procedure. Disease specific bother and health related quality of life questionnaires will be completed following consenting. As per standard of care, urinalysis and post-void residual volume will be measurement. The only assessment in this list that is not part of standard clinical care are the questionnaires. If patients are on medications for

overactive bladder, they will be required to stop at least 3 weeks prior to undergoing the baseline 3 day voiding diary.

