
Figure 1: Diagram showing sites of injections for patients undergoing 10 injections of 100 units of Botox®.

[figure not shown]

Figure 2: Diagram showing sites of injections for patients undergoing 20 injections of 100 units of Botox®

- At two weeks, the patient will return to clinic for a standard office visit. She will have a post void residual checked using either a bladder scan or catheter, and a urinalysis (urine culture will be sent per clinic protocol). If a urine culture grows any bacteria, and the patient is symptomatic, she will be treated with culture specific antibiotics. She will then be asked about symptoms of a urinary tract infection, if they have been treated for a urinary tract infection, difficulty emptying the bladder, or required intermittent or an

indwelling Foley catheter since the Botox® therapy. Subjects will complete the PGI-C and the OAB-SF. The patient will be sent home with a 3-day bladder diary to complete just prior to the 12-week visit.

- At 12 weeks, the patient will return to clinic and her 3-day bladder diary will be reviewed. A post void residual volume will be checked using either a bladder scan or catheter, and a urinalysis will be sent per standard practice (urine culture will be sent per clinic protocol). If a urine culture grows any amount of bacteria and the patient is symptomatic, she will be treated with culture specific antibiotics. She will then be asked about symptoms of a urinary tract infection, if they have been treated for a urinary tract infection, difficulty emptying her bladder, or required intermittent or an indwelling Foley catheter since the Botox® therapy. She will again take the OABq-SF and PGIC.
- Setting:
 - This study will take place at two Urology clinic locations at Wake Forest Baptist Medical Center, [name] in Winston Salem, NC and [name] in Greensboro, NC.

Subjects Selection Criteria

- Inclusion criteria: Subjects must meet the following inclusion criteria in order to be eligible for the study
 - 1. Female gender
 - 2. At least 18 years of age
 - 3. Have already decided to undergo intradetrusor Botox® injections for treatment of refractory overactive bladder.
 - 4. Able and willing to learn clean intermittent catheterization (or care provider is willing and able to perform intermittent catheterization).
 - 5. Understands and is willing to undergo follow up and complete questionnaires as described in this protocol
 - 6. Able to give informed consent

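### Women with earlier intradetrusor Botox may enter, and neither the design nor the analysis accounts for it: lost precision for pain, a possibly distorted baseline for the diary responder endpoint

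*Protocol*

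**What the plan says.** Two eligibility items in the protocol (Subjects Selection Criteria) bear on earlier toxin exposure, apart from an exclusion for allergy to it:

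- Inclusion item 3: "Have already decided to undergo intradetrusor Botox® injections for treatment of refractory overactive bladder". It is not limited to a first treatment.
- Exclusion item 4: "Treatment with Botox® toxin for other conditions". Toxin given earlier into the bladder for overactive bladder is not mentioned.

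The definition of refractory disease (Methods and Measures, Design) rests on persistent symptoms and on failure of, or unsuitability for, oral drugs. It is silent on toxin.

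The only washout is for oral overactive bladder drugs: "they will be required to stop at least 3 weeks prior to undergoing the baseline 3 day voiding diary".

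Allocation uses "random sequence number generation in blocks of 10", with no stratification factor stated. The Calendar of Events lists a Study Inclusion Form at baseline but no item on earlier toxin. The primary analysis compares unadjusted mean pain scores between arms. The SAP names two-group tests and descriptive statistics, with no covariate.

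**The concern.** The protocol takes women off oral drugs before the baseline diary. It says nothing comparable about the study drug itself when it has already been given into the same bladder. Two consequences follow if repeat patients enter.

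- **Pain (primary).** A woman who has been through the awake procedure before may rate it differently from a first-time patient. Pooling both kinds of patient without adjustment leaves that difference in the error term of a small trial.
- **Diary response (secondary).** Success is a reduction of more than 50% in urge incontinence episodes from the baseline diary to 12 weeks. Residual benefit from an earlier session would lower the baseline. The woman could then be classed as a failure for a reason unrelated to her arm.

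**Working it through.** **1. The plan's own sample size.** The protocol (Sample Size) states "we will assume an effect of size of 1" and SD 2, which is a difference of 2 points. Alpha and power are not stated; I assume 0.05 two-sided and 80%.

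n per arm = 2 × (1.960 + 0.842)² × 2² / 2² = 15.7, rounded up to 16. With 20% dropout, 16 / 0.8 = 20. Both stated figures reproduce. Exact t-test power at 16 per arm is 78.1%.

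**2. Share of pain variance due to prior exposure.** Let p be the share of repeat patients and d the difference in their mean score. Neither is in the documents, so both are assumed. The variance contributed is p(1 − p)d², set against the planned 2² = 4.

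| p | d | p(1 − p)d² | share of 4 |
|---|---|---|---|
| 0.5 | 1 | 0.25 | 6% |
| 0.5 | 1.5 | 0.5625 | 14% |
| 0.5 | 2 | 1.00 | 25% |
| 0.1 | 1 | 0.09 | 2% |

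**3. Is chance imbalance a further error?** With 20 per arm and p = 0.5, the between-arm difference in the proportion of repeat patients has SD √(0.25 × 2/20) = 0.158. For d = 1.5 this is 0.24 points, with variance 0.0563. The planned variance of the difference in means is 4 × 2/20 = 0.40. The ratio is 0.0563 / 0.40 = 14%, the same share as in step 2. Chance imbalance is therefore part of the ordinary standard error and must not be counted twice.

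**4. What adjustment could gain.** If the variation lies within the planned SD of 2, adjustment for p = 0.5 leaves a residual SD of √(4 − 0.25) = 1.94, √(4 − 0.5625) = 1.85 or √(4 − 1) = 1.73. Power at 16 per arm rises from 78% to about 81%, 84% or 88%. The degree of freedom spent changes these figures by about 0.1 point.

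If the variation comes on top of SD 2, the total SD is 2.06, 2.14 or 2.24, and unadjusted power falls to about 76%, 73% or 69%. The documents do not say which case applies.

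**5. How a lower baseline acts on the responder rule (figures assumed).** Take a woman with 2 episodes a day at 12 weeks.

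- Baseline 5: (5 − 2)/5 = 60%, a success.
- Baseline 4 (20% lower through residual effect): 50%, not above the threshold.
- Baseline 3 (40% lower): 33%, a failure.

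This shows the direction only. How many women would be affected, and by how much, cannot be derived from the documents.

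**The case against.** - **The pathway reads like first treatment.** Subject Recruitment Methods describes women being counselled on three options and then choosing toxin, and inclusion item 4 speaks of learning catheterisation. That is a fair reading, but neither text excludes a woman who has had toxin before.
- **Residual effect at entry is limited.** The refractory definition requires persistent symptoms, and a PVR above 150 cc is an exclusion. This stands as a partial limit. A woman can have persistent but reduced symptoms and a PVR below that figure.
- **The history may be collected anyway.** The content of the Study Inclusion Form is not shown, and the SAP does not list its clinical characteristics. This stands: one can say only that the documents require no such record, not that repeat patients would go unidentified.
- **Randomisation takes care of it.** For bias in the pain comparison, this stands. A reader might infer that an uneven mix of repeat patients biases the primary result, but step 3 shows that such imbalance is ordinary sampling error. What remains is precision that adjustment could recover.

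Other stronger readings also lack support. A reader might suppose that experienced patients would see through the 20-count masking; nothing in the documents shows this, and local and intravesical anaesthetic is given. A reader might extend the baseline problem to OABq-SF and PVR, but the Statistical Analysis section compares OABq-SF group means, and PVR is an endpoint at 2 and 12 weeks. Only the diary responder endpoint clearly depends on baseline. Finally, a reader might treat the 12-week assessment as the end of toxin effect and use it as a cut-off. A design that measures efficacy at 12 weeks implies an effect lasting at least that long, so it gives no upper limit.

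**Conclusion.** The gap is real and its consequences are modest. The visible criteria admit women with earlier intradetrusor Botox, and no stated part of the design or analysis takes this into account.

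For the primary pain score, the cost is precision. The share of planned variance is about 6% to 25% if half the women are repeat patients differing by 1 to 2 points, and about 2% if a tenth differ by 1 point. These figures rest wholly on the assumed prevalence and shift.

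For the diary responder endpoint, residual effect could make success harder to reach for a repeat patient. A reader might want to turn this into a figure for the diluted arm difference. That would need the share of women with residual effect, their chance of responding and the true response rates, and the documents give none of these.

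The change is worth making because it is cheap, not because the trial's conclusion is known to be at risk.

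**What to change.** 1. Record from the chart the number and date of earlier intradetrusor toxin sessions for each woman, on the Study Inclusion Form if it does not already ask for them.
2. State in the SAP that the between-arm NPRS comparison is a linear model with arm and prior exposure (yes/no).
3. Repeat the NPRS and diary-responder comparisons in first-time patients as a stated sensitivity analysis.
4. The SAP is written in the past tense. If outcomes have already been seen, label items 2 and 3 post hoc.

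The cost is one chart item per woman and one degree of freedom. The sensitivity set will be small: if half the women are repeat patients, about 20 of 40 remain, so it can check direction but not confirm an effect. Eligibility, enrolment and clinical care are unchanged.
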